# **PROTOCOL VERSION NUMBER AND DATE**

Version Stage	Versions No	Version Date	Protocol updated & finalised by;	Detail the key protocol update
Current	1.0	15.05.2025	[name]	Original application
Previous				

# **1 LIST OF ABBREVIATIONS AND DEFINITIONS**

AWS	Amazon Web Services			
CI	Chief Investigator - The overall lead researcher for a research project			
	(Outside the UK the term Coordinating Investigator or Investigator			
	may be used). Chief investigator is responsible for the overall conduct			
	of a research project.			
COSHH	Control of Substances Hazardous to Health			
CRF	Case Report Form			
CRN	Clinical Research Network			
GDPR	General Data Protection Regulation			
GP	General Practitioner			
GSTT	Guy's and St Thomas NHS Foundation Trust			
HRA	Health Research Authority			
HSE	Health and Safety Executive			
ICF	Informed Consent Form			
ICU	Intensive Care Unit			
IGA	Investigator Global Scale			
IPC	Infection Prevention Control			
NOSQ	Nordic Occupational Skin Questionnaire			
NHS R&D	National Health Service Research & Development			
OSF	Open Science Framework			
PI	Principal Investigator- An individual responsible for the conduct of the			
	research at a research site. There should be one PI for each research			
	site. In the case of a single-site study, the chief investigator and the PI			
	will normally be the same person.			
PIN	Participant Identification Number			
PIS	Participant Information Sheet			
PPI	Patient and public involvement			
Participant	An individual who takes part in a clinical trial			
PPI	Patient Public Involvement			
SAE	Serious Adverse Event			
SCIN	Skin Care Intervention in Nurses			
SOP	Standard Operating Procedure			
Sponsor	The organisation or partnership that takes on overall responsibility for proportionate, effective arrangements being in place to set up, run and report a research project.			

**NHS Foundation Trust** 

- SSA Site Specific Assessment
- TMF Trial Management File
- UK United Kingdom
- WHO World Health Organisation

# NHS Foundation Trust

#### SUMMARY/SYNOPSIS

Title	Assessing the feasibility, acceptability, and effectiveness of using a hand dermatitis self-assessment screening questionnaire in a workplace health surveillance programme	
Protocol Short Title/Acronym	Digital skin surveillance of healthcare workers in National Health Service	
IRAS Number	284234	
REC Reference		
EDGE reference	176025	
Study Duration	12 months	
Health condition(s) or problem(s) studied	Dermatitis	
Primary objective	
 
Can a self-assessed hand dermatitis screening questionnaire for at-risk healthcare workers reliably be used as part of a health surveillance programme?
 
What is the sensitivity and specificity of the hand dermatitis self-assessment screening questionnaire in identifying early hand dermatitis, and is it similar across all Fitzpatrick skin phototypes and occupational (clinical vs non-clinical) groups?
 
Is the self-assessment screening questionnaire and photographic method acceptable and feasible to use in healthcare staff in a busy NHS setting?
 
	
Secondary objective (s)	n/a	
End of study definition	All data collected, all queries are resolved and database locked	
Number of Participants	1386 (462 per site)	
Study Type	Cross-sectional questionnaire with follow-up tele-dermatology	
Human Tissue Samples (if applicable)	n/a	
Data collected/storage (if applicable)	During the study, study data will be collected and stored on the REDCap database and data files will be pseudonymised at the point of download so only participants study ID number and no other identifying information is on the file. This pseudonymised file will form the main dataset for analysis and will be sent to [name] (statistician: email: [contact]) and stored locally at the University of Southampton during the data analyses phase.	
	Additionally, the separate personal data extracted at the time of download will be removed from the main data file. Included in this contact information data file will be each participant unique study ID, and this will be used to link participant's contact information back to their response. Personal data will be deleted within 2 years of the end of the study.	

All digital records will be kept in a secure Guy's and St Thomas NHS Foundation Trust shared computer drive which is restricted to authorised research staff only.
At the end of the study, the data files will be downloaded on to two encrypted USB sticks and will be held in a secure location (i.e. locked and restricted access) within the OH department. for a period of two years.

**NHS Foundation Trust** 

#### 2 INTRODUCTION

Occupational hand dermatitis is the most frequently recognized occupational skin disease in the United Kingdom, with an estimated 84,000 people experiencing dermatitis caused or made worse by their work. (1-3) It is a particularly important occupational disease in healthcare workers. The 1-year prevalence of self-reported hand dermatitis in healthcare workers in Sweden (9051 workers) and in Norway (2274 workers) was estimated to be 21%. This compares with <10% in the general population. (4) The point prevalence of hand dermatitis (as diagnosed by hand photography) in a sample of 1599 nurses in the UK, was estimated to be 15% (13% in student nurses and 17% in ICU nurses). (5) Once an individual has developed irritant contact hand dermatitis the prognosis is poor. In a 15-year follow-up study of a Swedish general population sample, about a third of those with hand dermatitis needed on-going medical treatment and 5% experienced long periods of sickness absence, loss or change of job, or retirement from ill-health, as well as adverse economic implications. (6-7) Affected individuals may also experience negative psychosocial consequences, such as sleep disturbance and interference with leisure activities. (8)

There is a statutory responsibility under the COSHH Regulations 2002 for employers to carry out health surveillance for hand dermatitis in workers exposed to a known hazard in the workplace and where there is potential for significant exposure.(9) As many healthcare workers are unavoidably exposed to frequent wet work in their roles due to frequent or prolonged contact with water, the Health and Safety Executive considers that they should be under regular high-level health surveillance.(10) The reality of introducing such a programme in the healthcare setting is a challenge, not least because it raises practical and logistical issues which need to be carefully considered; for example which questionnaire should be used for health surveillance or, who should do the visual inspection of a worker's skin if dermatitis is suspected? The Nordic Occupational Skin Questionnaire (NOSQ)(11) is a validated tool but even its short form is four pages long, rendering it impractical for use in a large health surveillance programme in the National Health Service. Consequently, the statutory requirement is frequently not enforced in the health service and hand dermatitis is often not picked up until relatively late in the disease, making it harder to treat and increasing the risk of them being unable to continue to work.

The single-item questionnaire has been used before. As a component of a large randomised trial (SCIN trial: Skin care intervention in nurses) of an intervention to prevent hand dermatitis in intensive care and student nurses, we tested the accuracy of NHS nurses' self-assessment of hand dermatitis, using a simple question screening tool ('In your opinion do you have hand/wrist dermatitis?' with answer options of yes/no or unsure); if they reported having dermatitis they were asked to state where on the hand / wrist the dermatitis was. We compared their self-assessment with assessment by dermatologists using hand photographs. (5) The method was feasible and acceptable, as was that employed by the Danish study of hairdressers' dermatitis who self-assessed hand dermatitis when using a screening questionnaire adapted from NOSQ. (12)

During the course of the SCIN trial we developed a standardised validated method of screening for hand dermatitis using photographic images.(13) Several other studies have indicated that diagnostic decisions based on photographic images of localized skin regions are comparable with face-to-face assessments by dermatologists, since it allows clinicians to zoom in on distinct skin areas where early signs of disease are present.(14,15) Previous

#### **NHS Foundation Trust**

teledermatology studies have also shown them to be flexible and feasible to deliver in large, geographically dispersed occupational groups with noteworthy cost-benefits.(16,17) It is important that we now test our screening tools in clinical staff other than intensive care nurses, and in non-clinical staff for example laboratory workers. We also need to ensure that our screening tools are equally effective when applied to all Fitzpatrick skin phototypes as there are challenges in recognising the typical clinical features of dermatitis in skin of colour, especially given that a high proportion of NHS workers have darker skin type. For the purpose of this study, we will use a slightly modified Fitzpatrick Skin-Type Chart tool.

We postulate that screening by a single-item questionnaire with follow-up of those reporting possible hand dermatitis by teledermatology using selfie hand photographs taken with a mobile phone camera, would be a novel, and time- and cost-effective, approach to optimise and improve health surveillance for hand dermatitis in healthcare staff. If our suggested method is found to be feasible, acceptable, and effective, it has the potential to revolutionise the early detection and management of hand dermatitis in the healthcare sector.

# **3 PATIENT AND PUBLIC INVOLVEMENT**

During development and conduct of the former SCIN trial, we appointed, as our PPI coinvestigator, an experienced NHS midwife ([name]) who had a history of occupational hand dermatitis on the study. In this role, [name] assisted the study team with developing the new digital hand photographic method and self-assessment questionnaire used in the SCIN trial.

During conduct of the present study, we sought feedback from several nurses when developing the study document (participant information sheet) to ensure it was suitably worded and their feedback comments were incorporated.

During preparation of the present study, we sought feedback from several nurses when developing the study document (participant information sheet) to ensure it was suitably worded and their feedback comments were incorporated. Additionally, during conduct of the present study we will request guidance and practical assistance from wider PPI members (i.e. NHS staff: matrons and department managers) to support delivery of the study within each participating department. In addition, the proposed study was present to our trust's Occupational Health Clinical Governance and Risk Management committee which comprises OH nurses, service managers and matrons and clinical director for their review and feedback.

At the end of the present study, we will convene a one-off stakeholder forum involving representatives from infection, prevention and control (IPC), occupational health, NHS Employers, and the regulatory body (Health and Safety Executive) to consider the findings of the study and recommendations for the wider adoption of the screening tool across the NHS if the results are favourable.

Additionally, during conduct of the present study, it is possible we will request support and assistance from wider PPI members (i.e. NHS staff: matrons and department managers) to support delivery of the study within each participating department.

At the end of the present study, we will convene a one-off stakeholder forum involving representatives from infection, prevention and control (IPC), occupational health, NHS

**NHS Foundation Trust** 

Employers, and the regulatory body (Health and Safety Executive) to consider the findings of the study and recommendations for the wider adoption of the screening tool across the NHS if the results are favourable.

# 4 TRIAL OBJECTIVES AND PURPOSE

#### 4.1 Research Questions

1. Can a self-assessed hand dermatitis screening questionnaire for at-risk healthcare workers reliably be used as part of a health surveillance programme?

2. What is the sensitivity and specificity of the hand dermatitis self-assessment screening questionnaire in identifying early hand dermatitis, and is it similar across all Fitzpatrick skin phototypes and occupational (clinical vs non-clinical) groups?

3. Is the self-assessment screening questionnaire and photographic method acceptable and feasible to use in healthcare staff in a busy NHS setting?

# 5 STUDY DESIGN & FLOWCHART

#### 5.1 Study Design and Methods

This is a cross-sectional questionnaire of workers at risk of developing occupational hand dermatitis, with teledermatology using selfie hand photographs taken with a mobile phone camera.

## 6 PARTICIPANT SELECTION

#### 6.1 Setting

We have selected three NHS Trusts in different geographical regions of the UK and where staff are from a diverse range of ethnic origins and are likely to have a spread of Fitzpatrick skin phototypes: Aneurin Bevan University Health Board (Wales), Guy's and St Thomas' NHS Foundation Trust (England), and University Hospital of Leicester NHS Trust.

#### 6.2 Participant inclusion criteria

NHS staff (clinical and non-clinical) who are at increased risk of developing occupational hand dermatitis, here defined as staff who on average wash their hands with soap and water for a minimum of 10 times a day at work.(18) Examples of staff we will include are nurses (with the exception of ICU nurses - as this occupational group were part of the original SCIN study) (19), operating department practitioners, mortuary staff, clinical scientists and bench staff working in laboratories. We will aim at recruiting participants representing different skin phototypes.

Additionally, to be eligible participants will need to employed by the participating NHS organisation, have access to a smart phone or tablet device for the purpose of taking and sending in hand photographs AND have a valid NHS email address.

Participants must be aged between 16 and 80 years.

#### 6.3 Participant exclusion criteria

Individuals with current dermatitis as diagnosed by a medical practitioner, individuals who have used topical steroid cream to their hands in the past six weeks, visiting or temporary personnel who are undertaking duties on NHS premises including students on placements,

NHS Foundation Trust

contractors and anyone not directly employed by the participating NHS organisation. Individuals on long term sick leave (4 weeks or longer)

# 7 STUDY PROCEDURES

#### 7.1 Screening Procedures

With the assistance of Trust departmental managers and occupational health services, we will identify a minimum of six departments at each site where staff are known to engage in frequent hand washing and therefore have an increased occupational risk of dermatitis. As above, these departments will comprise a mix of patient-facing areas (wards) and other clinical settings (laboratories and mortuary).

In collaboration with departmental managers and with the support from local occupational health departments and Clinical Research Network (CRN) research delivery staff, we will distribute an information flyer (poster) to promote the study to eligible staff working in the selected departments. The study manager will work with clinical leads (department/ward managers) to develop a targeted approach to ensure participants' engagement with the study. This will include promotion of the study at team meetings, in the OH department and in communal staff rooms followed by provision (sent by the clinical leads via email) of an electronic participant information sheet (PIS) which will contain a link (including QR code) to the secure REDCap (eCRF) data collection portal.

A non-probability (convenience) sampling approach will be used to screen and recruit participants to the study. Accordingly, the study will be promoted to all staff from each participating department/unit.

No personal information will be reviewed or screened during the process of promoting the study to staff. If staff are interested in taking part, they will be encouraged to access study material (additional copy of the participant information sheet and consent form) via the online questionnaire platform using the link in the PIS or by using the study's QR code printed on posters and flyers. Note: Study documents (PIS, consent form and questionnaire) will be made available in Welsh upon request.

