## **12 STATISTICAL CONSIDERATIONS**

The following outlines the proposed statistical analyses methods planned as they relate to each research question (RQ).

• RQ1 Can a self-assessed hand dermatitis screening questionnaire for at-risk health care workers reliably be used as part of a health surveillance programme?

As the primary study outcome, we will calculate the sensitivity of the proposed selfassessment screening tool (single-item self-reported dermatitis) along with its 95% confidence intervals when compared with the gold standard (nurse's dermatitis assessment from the hand photographs). We will further assess its specificity, positive and negative predictive value. The analysis will be conducted for all participants and then separately by medium and high risk of hand dermatitis, determined by frequency of hand washing 10-20 times per day (medium risk), and more than 20 times per day (high risk).

• RQ2 What is the sensitivity and specificity of the hand dermatitis self-assessment screening questionnaire in identifying early hand dermatitis, and is it similar across all Fitzpatrick skin phototypes and occupational (clinical vs non-clinical) groups?

The accuracy of hand dermatitis self-assessment screening questionnaire will further be explored in sub- groups of our sample participants. Primarily sensitivity, and specificity, and further positive and negative predictive values, as indicators of the accuracy of the screening test will be estimated for clinical and non-clinical staff and their differences will be compared statistically. Due to the high number of NHS staff of non-white ethnic origin, and the lack of information about hand dermatitis or ability to self-report its presence across the six Fitzpatrick skin phototypes, we will also stratify our results by Fitzpatrick phototypes, with a potential to identify skin phototypes in which accuracy of the screening questionnaire is lower.

• RQ3 Is the self-assessment screening questionnaire and photographic method acceptable and feasible to use in healthcare staff in a busy NHS setting?

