#### 12.1 Statistical power

Considering as the primary study outcome the sensitivity of the single-item questionnaire (with secondary outcomes being its specificity, positive and negative predictive value) we enquired six occupational physicians with experience in NHS work what they would consider as the minimum acceptable sensitivity for such a self-assessment screening tool (single-item questionnaire) to be administered by managers to detect hand dermatitis in at risk healthcare workers. The majority (3 out of 4 who responded to our enquiry) reported a sensitivity of 80%. Assuming a prevalence of hand dermatitis among healthcare workers of 15%, and a high sensitivity of 0.90% with a width of confidence interval 0.10 (targeting a lower bound for sensitivity of 0.80), the estimated required sample size is 231. We hypothesised the same prevalence for clinical and non-clinical staff, and also for staff of light, medium and dark skin. This totals 1386 participants (i.e. 231 participants for each of the 6 groups clinical/non-clinical staff and type of skin), which would give sufficient power for any analysis stratification. We aim to recruit approximately equal numbers (~460 participants) from each of the 3 sites in the study.

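### The 1386 rests on six equal occupation-by-skin groups of 231, but recruitment has numeric targets only in total and per site, so the stated subgroup precision is not secured

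*Protocol*

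**What the plan says.** **Sizing (Protocol 12.1).** The primary outcome is the sensitivity of the single question. The inputs are a prevalence of 15% and "a high sensitivity of 0.90% with a width of confidence interval 0.10 (targeting a lower bound for sensitivity of 0.80", giving 231. This is multiplied to "231 participants for each of the 6 groups clinical/non-clinical staff and type of skin", total 1386. The section then asserts that this is enough power whichever way the analysis is stratified.

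**Recruitment (Protocol 7.1, 7.2, 12.1).** "A non-probability (convenience) sampling approach will be used to screen and recruit participants to the study". The study is promoted to everyone in the chosen departments, and eligible staff enter through a link. The numeric targets are 1386 overall and a per-site figure: "We aim to recruit approximately equal numbers (~460 participants) from each of the 3 sites in the study".

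**Unquantified aims.** Section 6.1 picks Trusts expected to have a range of phototypes. Section 6.2 aims for participants of different phototypes. Section 7.1 asks for at least six departments per site and a targeted approach to engagement.

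**Analysis (Protocol 12).** Accuracy is estimated for clinical and non-clinical staff, with a statistical comparison. It is stratified separately by the six Fitzpatrick phototypes, and by medium and high hand-washing frequency.

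**Losses (Protocol 7.3).** Participants whose photographs remain too poor to assess are left out of the final analysis.

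**Who is non-clinical.** The Introduction speaks of testing the tools in other clinical staff "and in non-clinical staff for example laboratory workers". Section 7.1 says "these departments will comprise a mix of patient-facing areas (wards) and other clinical settings (laboratories and mortuary".

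**The concern.** The total of 1386 delivers 231 per group only if half the participants are non-clinical and each half divides equally into light, medium and dark skin. Recruitment is balanced numerically on site, which is not one of the sizing factors. It is not balanced on occupation or skin group, which are.

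Research question 2 asks whether accuracy is similar across phototypes and occupational groups, and the Introduction names non-clinical staff and skin of colour as the evidence gap. If those groups come in small, their sensitivity will be imprecise. A wide interval could then be read as no evidence of lower accuracy, under a protocol that promised adequate size for any stratification. An analysis plan cannot restore participants who were not recruited.

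The boundary of one factor is also unclear. Laboratory workers are the Introduction's example of non-clinical staff, yet laboratories and mortuaries are listed in 7.1 under clinical settings. If those staff were coded as clinical, no department type named in 7.1 would supply the non-clinical group.

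**Working it through.** **Inputs.** 95% confidence (Section 12), so z = 1.96. From 12.1: prevalence 0.15; sensitivity 0.90 (printed with a stray percent sign); distance to the lower bound 0.90 − 0.80 = 0.10; six groups.

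**1. Reproduce the plan's figure.** n = z² × Se(1 − Se) / (d² × prevalence) = 3.8416 × 0.09 / (0.01 × 0.15) = 230.5, rounded up to 231. Then 6 × 231 = 1386. The 0.10 is thus a half-width; read as a full width it would give 922 per group. The arithmetic is right.

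**2. Slack.** Because 6 × 231 is exactly 1386, one person above 231 in any group leaves another short. If every recruit were equally likely to fall in each of the six groups, the chance that all reach 231 is about 3 in 100 million (0 of 200,000 simulated studies), and the smallest group averages about 212.

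**3. Unusable photographs.** Neither 231 nor 1386 is inflated, so any loss takes the average group below 231. As an illustration, an assumed 10% loss leaves 1247 evaluable, or 208 per group even with perfect balance.

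**4. One-way strata, as Section 12 analyses them.** For a stratum with share s of 1386 evaluable participants: n = 1386 s; cases = 0.15 n; half-width = 1.96 × √(0.09 / cases). The half-width reaches 0.10 when n is 231, so s must be at least 231/1386 = 16.7%. The shares below are assumptions.

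| Share | n | Expected cases | Half-width |
|---|---|---|---|
| 50% | 693 | 104 | ±0.06 |
| 33.3% | 462 | 69 | ±0.07 |
| 20% | 277 | 42 | ±0.09 |
| 16.7% | 231 | 35 | ±0.10 |
| 15% | 208 | 31 | ±0.105 |
| 10% | 139 | 21 | ±0.13 |
| 5% | 69 | 10 | ±0.18 |

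These use the plan's own normal approximation, which is optimistic with few cases. At a 10% share its lower bound is 0.77, while the Wilson lower bound is 0.70.

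**5. Six phototypes against three skin groups.** Six shares average 16.7%, exactly the minimum found in step 4. Unless all six phototypes are equally common, at least one falls below it.

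**6. Two-way groups, as 12.1 sizes them.** Expected n = 1386 × occupation share × skin share. With an assumed 30% non-clinical and 20% in the smallest skin group: n = 83, about 12 cases, ±0.17. With 50% and 20%: n = 139, about 21 cases, ±0.13. With 50% and 33.3%: n = 231 and ±0.10, the plan's case.

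**The case against.** The best defence is that the six-way group appears only in the sizing arithmetic. Section 12 stratifies by one factor at a time, and there the design is more forgiving: a non-clinical share of 20% would still give 277 people and ±0.09, inside the planned half-width. That stands, so the two-way figures show what 12.1 claims rather than harm to a stated analysis. It does not rescue the phototype analysis (step 5) or the assurance about any stratification.

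Convenience sampling is not itself an error, since it can run alongside group targets. That also stands; the fault lies in joining it to the 12.1 claim without such targets.

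A reader might infer several stronger points that the documents do not support:

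- *That the smaller groups will not be filled, or will be nearly empty.* A shortfall somewhere is practically certain, but which group and how large depend on a staff mix that the protocol does not give.
- *That nothing steers recruitment towards balance.* Sections 6.1, 6.2 and 7.1 do, though without numbers. The targeted approach in 7.1 concerns engagement rather than balance.
- *That recruitment stops once the total is reached.* Section 7.2 states an aim of 1386 and a period of up to nine months, with no closing rule.
- *That power to detect a given difference between occupational groups falls by a stated amount.* Section 12.1 sizes for precision and names no such difference. Any figure would depend on which group is assumed worse and on the variance formula.

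The laboratory wording may be partly innocent: 7.1 describes places, while the Introduction describes staff. It still needs settling, because the occupational comparison depends on it.

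**Conclusion.** The concern holds as a mismatch between the sizing statement and the recruitment plan. The calculation in 12.1 is correct, but its assurance depends on equal groups that the protocol neither targets nor monitors and for which it leaves no margin.

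The practical effect varies by analysis. The clinical versus non-clinical estimates keep the planned precision if the smaller side holds at least 16.7% of evaluable participants; with an assumed 10% photograph loss, that becomes 231/1247 = 18.5% of those recruited. The six-phototype stratification is the weak point: at least one phototype will almost certainly miss ±0.10, and an assumed share of 5% to 10% gives ±0.18 to ±0.13.

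These sizes rest on the protocol's prevalence of 15% and sensitivity of 0.90 in every stratum, and on shares that are assumptions. The absence of group targets is certain; the size of the shortfall is not. The overall sensitivity estimate is not affected by this point.

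**What to change.** 1. **Section 12.1.** Withdraw the statement that the total suffices for any stratification. Give instead the expected half-width for each stratum named in Section 12, over a plausible range of shares and net of an assumed proportion of unusable photographs. Say whether the skin strata are the three groups used for sizing or the six phototypes used for analysis.
2. **Sections 7.1 and 7.2.** Set minimum evaluable targets by occupation and by skin group. Review form 2 counts periodically, blind to dermatitis results, and direct promotion and the choice of further departments to groups that are running short. Convenience sampling can stay.
3. **Introduction, 6.2 and 7.1.** Classify laboratory and mortuary staff consistently as clinical or non-clinical.

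Occupation and skin phototype are already collected, so this needs wording and a recurring count rather than new data. The costs are more promotion effort, possibly slower recruitment in short groups, and a less favourable precision statement in 12.1. The changes are best made before recruitment opens.
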